1.1 Design methodology

1.1.1 *Research design and general methodological approach*

The planned research design is a double-blind, placebo-controlled randomized trial.

- A. Study arm: mifepristone 200 mg orally 18-24 hours prior to osmotic dilator placement
- B. Control arm: placebo oral medication 18-24 hours prior to osmotic dilator placement

The total number of women will be 66 and 33 women will be allocated to each group (Appendix – CONSORT Flow Diagram).

1.1.2 *Criteria for the selection of subjects*

Inclusion criteria:

- A. Women planning dilation and evacuation with cervical dilator placement at gestational ages 20 weeks 0 days to 23 weeks 6 days on procedure day
- B. English-speaking/writing

Exclusion criteria:

- A. Allergy to mifepristone
- B. Any condition that in the opinion of the investigator could impede study participation or collection of study data

1.1.3 *Subject recruitment and allocation*

Participant identification

Potential participants will be identified either at time of referral to UC Davis Family Planning Center from outside clinics after dating ultrasound is performed or when presenting directly for dating ultrasound at UC Davis Family Planning Center.

Pre-visit phone call

For women who have been referred to UC Davis and have already had a dating ultrasound, research staff will call to explain the study. For women not interested in the study, a standard pre-operative visit per clinic guidelines will be scheduled. For women who are

interested in enrolling in the study, a screening and enrollment visit will be scheduled.

Women will be notified that they will be randomly allocated to mifepristone or placebo medication.

1.1.4 *Description of the drugs and devices to be studied*

Mifepristone exerts anti-progestin activity by binding with high affinity to progesterone receptors and causing an increase in glycosaminoglycans, such as hyaluronic acid, increases collagenase activation and tissue water content ¹⁴⁻¹⁷. These actions promote softening and dilation of the cervix ^{14,15} and also increase the myometrial response to exogenous prostaglandins, such as misoprostol ¹⁷.

1.1.5 *Admission procedure*

Day 1: Screening and Enrollment

This visit is scheduled after a pre-visit phone call or at the time of the dating ultrasound visit. Pre-operative examination and operative consents will be reviewed and signed per usual practice. Research staff will review the study and obtain informed consent for the study. Office or formal radiologic ultrasounds will be performed based on clinical indication. Study medication will then be dispensed with instructions to take 18-24 hours prior to scheduled pre-operative visit. All women will receive a diary to collect side effect information.

Day 2: Pre-operative visit

Women will return for their scheduled pre-operative visit the day prior to their scheduled procedure. Diaries will be collected and reviewed and osmotic dilators (Dilapan-S 4-mm) will be placed. Pain score measured by VAS will be collected at time of dilator placement.

Day 3: Standard dilation and evacuation procedure

Participants will proceed to the operating room and undergo sedation per anesthesia guidelines. Initial cervical dilation using Pratt dilators will be measured after dilator removal. Standard dilation and evacuation will be performed.

1.1.6 Follow-up procedure

There will be no follow-up necessary and the end of the procedure will indicate study completion.

1.1.7 Criteria for discontinuation

Women who report not taking the study medication will be discontinued from the study.

Participants may discontinue from the study for any reason.

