1.1.10 Data analysis

As the primary outcome is a dichotomous variable, I will perform logistic regression analyses. The number of cervical dilators will be collected either at time of clinic visit or by chart review. Missing data will be minimized by allowing for exclusion of any potential participant who may be judged to have increased risk for loss to follow up at time of enrollment and prior to randomization. We will include all women randomized and perform intent-to-treat analysis with no apparent exclusions. In addition, a second analysis will be conducted excluding women who do not report ingesting the study medication.

At time of enrollment, we plan to collect baseline demographic data, including age, race, ethnicity, education level, obstetric history, and history of cervical procedures. I will perform univariate analyses to compare the two study groups at baseline. If any variables are significantly different, I will utilize those variables to adjust the logistic regression for the primary outcome. While not powered to detect a statistically significant difference among the two groups for the secondary outcomes, exploratory analyses will be performed to identify possible trends and areas of interest for a subsequent larger trial. The data analysis will be as follows:

Secondary outcome	Data analysis plan
Proportion of appropriate number of dilators	Logistic regression
Cervical dilation at time of procedure	Linear regression
Number of tablets of ibuprofen and Tylenol #3 utilized with dilators in place	Logistic regression
Proportion of women requiring mechanical dilation at time of procedure	Logistic regression
Pain at time of dilator placement (VAS)	Linear regression
Provider perception of overall ease of procedure	Logistic regression
Provider perception of difficulty in dilating the cervix when required	
Overall complication and adverse event rate	Logistic regression

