1.1.11 Number of subjects and statistical power

	Control group
--	---------------

% with +2 dilators	1	5	10	15	20
Study group	10	242	950	--	--
	20	100	176	438	1864
	30	60	86	144	268
	35	50	68	102	166
	40	42	54	76	114
	45	36	44	60	84
	50	30	38	50	66
	60	24	28	34	44
	70	18	22	26	30
	80	14	16	20	22

The appropriate number of dilators is based on gestational age at this university:

- a. 20 weeks 0 days to 20 weeks 6 days: at least 5 dilators
- b. 21 weeks 0 days to 21 weeks 6 days: at least 6 dilators
- c. 22 weeks 0 days to 23 weeks 6 days: at least 7 dilators

Without adjunctive medications, it is assumed that placing two more than the standard number of dilators will be difficult and a rare occurrence in about 10% of women. With adjunctive preparation with mifepristone, dilator placement will lead to an increased proportion of women (45%) receiving two additional dilators than the indicated number. We require 60 participants to detect a difference of 35% between the two groups and maintain 80% power and an alpha of 0.05. To account for medication nonadherence, we plan to recruit 10% more patients for a total of 66 women.

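### Section 1.1.7 takes women who report non-intake out of the study, while the intent-to-treat analysis in 1.1.10 needs their outcomes; the two sections should be reconciled

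*Combined protocol and SAP*

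**What the plan says.** Section 1.1.7 has two sentences. The first is "Women who report not taking the study medication will be discontinued from the study". The second is "Participants may discontinue from the study for any reason". The first speaks of the study, not of treatment, and nothing in the section says that data collection goes on afterwards.

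Section 1.1.10 defines two analyses. The main one is "We will include all women randomized and perform intent-to-treat analysis with no apparent exclusions". For the other, "a second analysis will be conducted excluding women who do not report ingesting the study medication".

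On data sources, 1.1.10 says: "The number of cervical dilators will be collected either at time of clinic visit or by chart review". It also plans to limit missing data by allowing exclusion of women "judged to have increased risk for loss to follow up at time of enrollment and prior to randomization".

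On timing, 1.1.5 dispenses the drug on Day 1. At the Day 2 visit, "Diaries will be collected and reviewed and osmotic dilators (Dilapan-S 4-mm) will be placed", and the VAS pain score is taken at placement. Cervical dilation is measured on Day 3. Section 1.1.6 plans no later follow-up.

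**The concern.** Whether a woman took the tablet is known only after randomization. An intent-to-treat analysis of all randomized women needs outcomes from those who did not take it, and the second analysis differs from the first only if those outcomes exist. A coordinator who follows 1.1.7 to the letter may stop collecting the data that the analyst following 1.1.10 needs.

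The schedule makes the loss possible. Non-intake could come to light when the diary is reviewed on Day 2, before the dilator count, the pain score or any Day 3 outcome has been recorded. With no later visit, a pain score or provider rating not taken at the time could not be obtained at a further study contact. The exclusion of women at risk of loss to follow-up acts before randomization, so it does nothing for a woman discontinued on Day 2.

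At stake is whether the primary analysis is made on the population the plan names, or in effect on women who reported taking the drug.

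**Working it through.** **1. Which outcomes are exposed**

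| Outcome | When it arises | Stated source after discontinuation |
|---|---|---|
| Dilator count (primary) | Day 2 | Chart review is allowed in 1.1.10, but not tied to discontinued women |
| VAS pain (exploratory) | Day 2 | None in the visible text |
| Tablet counts (exploratory) | While dilators are in place | None in the visible text |
| Provider ratings (exploratory) | Day 3 | None in the visible text |

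**2. Inputs for the illustration**

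- Rates of 45% (study) and 10% (control), from 1.1.11.
- 33 women per arm, from 1.1.1.
- Number lost per arm, *k*. The documents give no expected nonadherence rate, so *k* = 1, 2 and 3 are assumptions. The largest is taken from the allowance in 1.1.11: "To account for medication nonadherence, we plan to recruit 10% more patients for a total of 66 women". This reproduces as 60 × 1.10 = 66, which is 6 extra women, or 3 per arm.
- The planned rates are assumed to hold among the 33 − *k* women observed in each arm, and the lost women's counts are assumed not to be recovered.

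**3. Central case: non-takers respond equally in both arms**

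If non-takers respond at a common rate *r*, then *r* cancels from the difference:

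Difference = [0.45(33 − k) + rk]/33 − [0.10(33 − k) + rk]/33 = 0.35 × (33 − k)/33

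- *k* = 1: 35 × 32/33 = 33.9 points
- *k* = 2: 35 × 31/33 = 32.9 points
- *k* = 3: 35 × 30/33 = 31.8 points

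The women observed would show 35 points in each case.

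**4. Extreme bounds**

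Lower bound (all lost controls positive, all lost study-arm women negative) = [0.45(33 − k) − 0.10(33 − k) − k]/33

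Upper bound (the reverse) = [0.45(33 − k) + k − 0.10(33 − k)]/33

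| *k* per arm | Lower | Equal response | Upper |
|---|---|---|---|
| 1 | 30.9 | 33.9 | 37.0 |
| 2 | 26.8 | 32.9 | 38.9 |
| 3 | 22.7 | 31.8 | 40.9 |

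For *k* = 3 the lower bound is (13.5 − 3 − 3)/33 = 7.5/33 = 22.7 points, and the upper bound is (13.5 + 3 − 3)/33 = 13.5/33 = 40.9 points.

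**5. How extreme the lower bound is**

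If lost women in both arms respond at the 10% control rate, the lower-bound pattern for *k* = 3 has probability 0.10³ × 0.90³ = 0.0007.

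An example in whole women, with likelihood-ratio p values and all three lost study-arm women counted as negative:

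| Study | Control | Lost controls counted positive | p |
|---|---|---|---|
| 13/30 | 3/30 | observed women only | 0.003 |
| 13/33 | 4/33 | 1 of 3 | 0.010 |
| 13/33 | 5/33 | 2 of 3 | 0.025 |
| 13/33 | 6/33 | 3 of 3 | 0.055 |

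Only the last row crosses 0.05.

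**The case against.** The strongest reply is that 1.1.10 already settles the matter for the primary outcome. It names all randomized women, it defines a second analysis that makes sense only if the first keeps non-takers, and it gives a chart-review route that works after randomization. Dilator placement belongs to the scheduled pre-operative visit, so a woman who has left the study may still have a count in her chart. Most of this stands. It makes loss of the primary outcome avoidable and probably uncommon. It does not remove the conflict, because nothing says chart review applies to women discontinued under 1.1.7.

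The timing is also partly inferred. Section 1.1.5 describes the diary as a record of side effects and does not say when or how intake is asked. That stands too: loss before the Day 2 outcomes is possible, not certain.

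A reader might infer that the primary comparison will be biased between arms. The documents do not support that. The trial is double-blind, and women who never took a tablet have had no drug effect, so there is no evident reason for non-intake, or for non-takers' response, to differ by arm. The likelier effects are some loss of precision and a shift of the target towards takers.

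Finally, the outcomes with no stated recovery route are exploratory and, as 1.1.10 says, not powered. That limits the weight of the point.

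**Conclusion.** The conflict is real. Read literally, 1.1.7 removes from the study women whom 1.1.10 keeps in its main analysis. It should be fixed, but it does not undermine the design, and no figure in the plan is wrong because of it.

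With 3 women per arm lost and not recovered, the all-randomized difference would be about 31.8 points rather than 35 if non-takers respond equally in both arms. The range of 22.7 to 40.9 points marks the limits of what is possible and is not a forecast. All of this rests on the planned rates holding among the women observed, on an assumed number lost, and on counts not being recovered. With full recovery of counts the uncertainty is zero.

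Two further readings go too far. One is that the second sentence of 1.1.7 is also at fault: a participant's freedom to leave for any reason contradicts nothing in 1.1.10. The other is that the conflict shows the 66 women to be too few: keeping non-takers under observation changes no stated sample-size figure.

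**What to change.** Replace only the first sentence of 1.1.7, for example with:

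> *A participant who reports non-intake of study drug stays in the study for outcome collection. Her dilator count (from the chart if necessary) and the planned Day 2 and Day 3 outcomes are recorded and enter the intent-to-treat analysis.*

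Leave the second sentence of 1.1.7 as it stands. Sections 1.1.10 and 1.1.11 need no change. The edit concerns data collection only and sets no rule for clinical care.

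The cost is one sentence, plus slight extra data collection at visits already scheduled for the women who report non-intake. No added enrolment is needed.

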1.1.8 Laboratory and other investigations

Not applicable

1.1.9 Data management

Each participant will be assigned a file in a locked cabinet of a locked office. Participant files will contain signed consent forms, study allocation number, and paper copies of data collection forms.

1.1.10 Data analysis

As the primary outcome is a dichotomous variable, I will perform logistic regression analyses. The number of cervical dilators will be collected either at time of clinic visit or by chart review. Missing data will be minimized by allowing for exclusion of any potential participant who may be judged to have increased risk for loss to follow up at time of enrollment and prior to randomization. We will include all women randomized and perform intent-to-treat analysis with no apparent exclusions. In addition, a second analysis will be conducted excluding women who do not report ingesting the study medication.

At time of enrollment, we plan to collect baseline demographic data, including age, race, ethnicity, education level, obstetric history, and history of cervical procedures. I will perform univariate analyses to compare the two study groups at baseline. If any variables are significantly different, I will utilize those variables to adjust the logistic regression for the primary outcome. While not powered to detect a statistically significant difference among the two groups for the secondary outcomes, exploratory analyses will be performed to identify possible trends and areas of interest for a subsequent larger trial. The data analysis will be as follows:

Secondary outcome	Data analysis plan
Proportion of appropriate number of dilators	Logistic regression
Cervical dilation at time of procedure	Linear regression
Number of tablets of ibuprofen and Tylenol #3 utilized with dilators in place	Logistic regression
Proportion of women requiring mechanical dilation at time of procedure	Logistic regression
Pain at time of dilator placement (VAS)	Linear regression
Provider perception of overall ease of procedure	Logistic regression
Provider perception of difficulty in dilating the cervix when required	
Overall complication and adverse event rate	Logistic regression

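### Chance differences between the randomized arms at baseline decide which covariates enter the primary logistic regression, so the primary odds ratio is not fixed in advance

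*Combined protocol and SAP*

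**What the plan says.** Section 1.1.1 sets the design: "The planned research design is a double-blind, placebo-controlled randomized trial". Section 1.1.10 gives the primary method: "As the primary outcome is a dichotomous variable, I will perform logistic regression analyses". It then lists what is recorded at baseline: "At time of enrollment, we plan to collect baseline demographic data, including age, race, ethnicity, education level, obstetric history, and history of cervical procedures". That is six named items in an open list. Two sentences follow on their use: "I will perform univariate analyses to compare the two study groups at baseline" and "If any variables are significantly different, I will utilize those variables to adjust the logistic regression for the primary outcome".

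The section gives no significance level for the baseline tests and no fixed covariate. It does not say that the unadjusted model stays primary or that the adjusted one is a sensitivity analysis. The table of secondary outcomes names model types only. Section 1.1.11 sizes the trial on a comparison of two proportions: "We require 60 participants to detect a difference of 35% between the two groups and maintain 80% power".

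**The concern.** Under randomization, a significant baseline difference says nothing about whether a variable predicts the outcome. A rule that selects on imbalance will usually leave out a prognostic variable and will sometimes bring in an irrelevant one. The primary model, and with it the meaning of the primary estimate, then depends on the draw of the randomization.

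Two things can move the odds ratio when a covariate enters:

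- Chance imbalance in sparse data, which matters here because few events are expected.
- Non-collapsibility: the odds ratio conditional on a prognostic covariate differs from the marginal one even without imbalance.

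At stake is a primary estimate that cannot be stated before the arms are compared. The trial is also sized on an unadjusted contrast and may report an adjusted one.

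**Working it through.** **Inputs from the document.** 33 women per arm (section 1.1.1). 10% vs 45%, 80% power, alpha 0.05, N = 60 raised to 66 (section 1.1.11). Six named baseline items (section 1.1.10).

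**The plan's own figure.** The two-sided, continuity-corrected two-proportion formula for 10% vs 45% gives 29.8, so 30 per arm and 60 in total, as stated; 60 × 1.10 = 66. The sample size therefore rests on an unadjusted comparison.

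**Sparseness.** Expected events: 33 × 0.10 + 33 × 0.45 = 3.3 + 14.85 = 18.15. Standard error of the unadjusted log odds ratio: √(1/3.3 + 1/29.7 + 1/14.85 + 1/18.15) = 0.678. The 95% interval extends exp(1.96 × 0.678) = 3.8-fold either way.

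**How often the rule acts.** With six independent tests at an assumed 0.05 level: 1 − 0.95^6 = 0.265. With pairwise correlation 0.3, 0.5 or 0.8 this falls to 24%, 21% or 14%. With 10 independent variables it would be 40%.

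**What it does to the estimate.** Simulation of the rule, 12,000 trials per setting, 33 per arm, 10% vs 45%. Assumed: age continuous; race and education with four levels; ethnicity, one obstetric item and cervical procedures binary with prevalence 0.35, 0.5 and 0.1; t and Pearson tests at 0.05. The obstetric item has an assumed odds ratio of 1, 4 or 8 with the outcome.

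| | OR 1 | OR 4 | OR 8 |
|---|---|---|---|
| At least one variable enters | 28.7% | 28.5% | 28.2% |
| Obstetric item enters | 6.8% | 6.3% | 5.9% |
| At least one of the other five enters | 23.4% | 23.7% | 23.6% |
| Adjusted/unadjusted OR, 5th–50th–95th percentile | 0.76–1.02–1.80 | 0.74–1.03–2.10 | 0.75–1.04–2.82 |
| Shift of 20% or more, when a variable enters | 34.1% | 40.2% | 42.6% |
| Shift of 20% or more, of all trials | 9.4% | 11.1% | 11.5% |
| Verdict changes, of all trials (Wald) | 1.6% | 2.0% | 2.3% |
| Verdict changes, of all trials (likelihood ratio) | 1.4% | 1.7% | 1.9% |
| Wald power, unadjusted → rule | 88.0 → 87.1% | 87.9 → 87.3% | 87.5 → 87.2% |
| Likelihood-ratio power, unadjusted → rule | 92.6 → 91.8% | 92.3 → 91.9% | 92.0 → 92.0% |

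Notes on the table:

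- The simulated entry rate (28.7%) is a little above the formula's 26.5%. The obstetric item alone enters in 6.8% rather than 5% of trials when it has no effect.
- The two shift rows do not multiply out exactly: 0.341 × 0.287 = 0.098, against 0.094. The gap is consistent with about 4% of triggered trials giving no finite odds ratio and so no ratio to compare.
- With race and education coded as two levels and no prognostic item, a variable enters in 30.2% of trials. The 5th to 95th percentile range is then 0.79 to 1.58, and 7.8% of all trials shift by 20% or more.

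**Type I error.** With 10% in both arms and no prognostic item, rejection goes from 0.5% to 0.8% (Wald) and stays at 6.8% (likelihood ratio). With six continuous covariates and 27.5% in both arms, the rule rejects in 3.9 to 4.7% of trials, against 4.4 to 4.8% unadjusted.

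**Non-collapsibility.** The marginal odds ratio is (0.45/0.55)/(0.10/0.90) = 7.36. Conditional on a binary covariate with outcome odds ratio 1, 2, 4 or 8 it is 7.36, 7.68, 8.64 or 10.34, that is × 1.00, 1.04, 1.17 or 1.40. Without a prognostic covariate there is no such effect.

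**The case against.** The strongest reply is that the rule is itself written down in advance and looks only at baseline data, never at the outcome, in a double-blind trial. This is not choosing a model by its result, and the calculations agree: type I error is not materially raised, power barely moves and the verdict seldom changes. The median shift is close to nil, and even the 0.76 to 1.80 range is modest beside an interval that runs 3.8-fold either way. All of that stands, and it limits the point to the definition of the estimate.

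Further points that stand in part:

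- The document never uses the term odds ratio, and section 1.1.11 speaks of a difference in percentages. The odds ratio is inferred as the usual effect measure of a logistic regression.
- The 0.05 test level, category counts, prevalences and covariate effects are assumptions. They set the size of the shift but not the fact that chance picks the model.
- Gestational age is missing from the six named items, but this is not in itself a defect. The list is open, the dilator threshold already varies with gestational age, and the document does not say whether it predicts the outcome.
- Comparing baseline data by arm is separable from adjusting on the result. Only the adjustment sentence has to go to fix the primary model.

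What the reply does not answer is that a stated rule which selects on chance imbalance still leaves the primary model unknown until the arms are compared, with no test level and an open list of candidates.

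**Conclusion.** The concern holds. As written, the primary odds ratio may be unadjusted or adjusted for any set of baseline variables, depending on chance. For six variables the rule acts in about 26% of trials (assumed 0.05 level, independence), or 14 to 24% under the correlations tried. With no prognostic covariate, about 8 to 9% of all trials would report a primary odds ratio moved by 20% or more, depending on how race and education are coded. If one obstetric item is truly prognostic (assumed odds ratio 4), the rule omits it in 94% of trials (100 − 6.3), yet admits at least one irrelevant variable in 24%.

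The effect on the test is small: no material added type I error, about 1 point of power or less, and a changed verdict in about 1.5 to 2% of trials (up to 2.3% with an assumed odds ratio of 8). The sample size is not affected. The point should be corrected because the primary estimate ought to be defined before the arms are compared, and correcting it costs almost nothing.

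**What to change.** Delete the sentence in section 1.1.10 that adjusts for significantly different variables, and report baseline data descriptively by arm. Before unblinding, name one primary model:

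1. treatment only, which matches the sample size calculation in section 1.1.11; or
2. treatment plus one named covariate chosen on clinical grounds, whatever the baseline comparison shows. Examples are one obstetric-history item, or gestational age, which is known for every woman through the inclusion criterion ("Women planning dilation and evacuation with cervical dilator placement at gestational ages 20 weeks 0 days to 23 weeks 6 days on procedure day") and sets the dilator threshold ("The appropriate number of dilators is based on gestational age at this university").

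Possible wording:

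> The primary analysis is a logistic regression of the primary outcome on treatment arm [and the named covariate] in all women randomized. No covariate will be added or removed because of a baseline comparison. The other model will be reported as a sensitivity analysis.

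**Cost.** Wording only; N and data collection are unchanged. Treatment-only gives up any gain from a prognostic covariate. In simulation (10,000 trials per setting), adding one pre-specified binary covariate with an assumed outcome odds ratio of 1, 2, 4 or 8 changed Wald power from 88.6 to 88.3%, 88.0 to 88.3%, 88.1 to 89.7% and 87.7 to 91.5%. A covariate that turns out not to be prognostic therefore costs about 0.3 points on the Wald test and nothing on the likelihood-ratio test (92.6% both ways). Differences of a few tenths of a point are close to simulation error.

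### No covariate is prespecified for the linear regression of cervical dilation, although the site's dilator minimum rises with gestational age; naming gestational age as a term is valid, nearly free and may sharpen the estimate

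*Combined protocol and SAP*

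**What the plan says.** The secondary-outcome table in section 1.1.10 pairs "Cervical dilation at time of procedure" with linear regression and says nothing about other model terms. VAS pain at dilator placement gets the same entry. The text above the table describes one adjustment rule: baseline variables that differ significantly between the arms are added to the logistic regression for the primary outcome. It is not extended to the secondary outcomes, which the section describes as unpowered and exploratory, meant to point to trends for a larger trial.

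The baseline data are introduced as including "age, race, ethnicity, education level, obstetric history, and history of cervical procedures". Gestational age is not named there, but section 1.1.2 makes it an eligibility criterion (20 weeks 0 days to 23 weeks 6 days on procedure day).

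Section 1.1.11 states: "The appropriate number of dilators is based on gestational age at this university". The minimum is 5 dilators in week 20, 6 in week 21 and 7 in weeks 22 and 23. Under section 1.1.5, dilation is measured with Pratt dilators on Day 3, once the osmotic dilators are out.

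**The concern.** The site's own rule builds a gestational-age gradient into cervical preparation: the minimum number of dilators rises from 5 to 7 across the eligible range, in both arms. Dilation after their removal can be expected to reflect some of that gradient. If gestational age is not in the model, whatever it explains stays in the residual and widens the interval for the treatment difference. Sections 1.1.1 and 1.1.3 describe no stratification by gestational age, so the design does not absorb it either.

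Precision is at stake, not validity. In a comparison meant to inform a larger trial, the width of the interval is most of what the reader gets.

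Silence about covariates also leaves their choice open until the data are seen. One tempting choice, the number of dilators actually placed, is measured after randomisation and underlies the primary outcome. Adjusting for it could remove part of any drug effect. Naming a baseline term in advance closes that gap.

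**Working it through.** **The plan's own figure.** The plan gives no calculation for cervical dilation, so the only figure to reproduce is the primary sample size. Inputs from section 1.1.11: control rate 10% ("a rare occurrence in about 10% of women"), study-arm rate 45% ("an increased proportion of women (45%) receiving two additional dilators than the indicated number"), and "maintain 80% power and an alpha of 0.05". Two-sided testing is assumed, since sidedness is not stated.

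- Mean proportion: (0.10 + 0.45)/2 = 0.275.
- Uncorrected n per arm: [1.96 × √(2 × 0.275 × 0.725) + 0.8416 × √(0.10 × 0.90 + 0.45 × 0.55)]² / 0.35² = 24.3, rounded up to 25.
- With continuity correction: (24.3/4) × [1 + √(1 + 4/(24.3 × 0.35))]² = 29.8, rounded up to 30.
- Total: 2 × 30 = 60, as stated ("We require 60 participants to detect a difference of 35% between the two groups"). Adding 10% gives 66, or 33 per arm.

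**Unadjusted precision for a continuous outcome.** With 33 per arm, the difference detectable with 80% power is (1.96 + 0.8416) × √(2/33) = 0.69 SD. The documents give no SD, so this stays in SD units.

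**Effect of one prespecified covariate.** Let R² be the share of within-arm variance in dilation that gestational age explains. The documents do not give it, so a range is shown. The unadjusted model leaves 66 − 2 = 64 residual degrees of freedom; adding gestational age leaves 63. Then:

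- Variance ratio, adjusted to unadjusted = (1 − R²) × 64/63.
- Standard-error ratio = square root of the variance ratio.
- Equivalent number of women = 66 / variance ratio.
- Detectable difference = 0.69 SD × standard-error ratio.

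| Assumed R² | Variance ratio | SE ratio | Change in SE | Equivalent women | Detectable difference (SD) |
|---|---|---|---|---|---|
| 0 | 1.016 | 1.008 | +0.8% | 65 | 0.70 |
| 0.05 | 0.965 | 0.982 | −2% | 68 | 0.68 |
| 0.10 | 0.914 | 0.956 | −4% | 72 | 0.66 |
| 0.20 | 0.813 | 0.902 | −10% | 81 | 0.62 |
| 0.30 | 0.711 | 0.843 | −16% | 93 | 0.58 |

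**Break-even.** The variance ratio equals 1 when R² = 1 − 63/64 = 0.0156, about 1.6%.

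**Cost of more terms.** A second covariate raises break-even to 1 − 62/64 = 3.1%. Each added term therefore needs its own support, and the documents supply it only for gestational age.

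**The case against.** The case for leaving the plan alone is substantial. Under randomisation the unadjusted difference is unbiased. The outcome is declared exploratory, and neither the primary analysis nor the sample size depends on it. The 0.69 SD detectable difference comes mainly from having 33 women per arm; an R² of 0.10 moves it only to 0.66. Eligibility covers about four weeks of gestation, which limits what gestational age can explain, and the larger gains need an R² of 20% to 30% for which the documents offer no basis. All of this stands. It limits the importance of the point, but does not remove an improvement that costs one degree of freedom.

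A reader might infer more than the documents support:

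- *That the plan rules out adjustment.* It does not. It names linear regression, which can carry covariates, and is silent on which ones.
- *That precision is certainly being lost.* This is not shown without an R². Below about 1.6% there is no gain.
- *That the same holds for VAS pain.* More dilators at later gestation make a link with placement pain conceivable, but the dilator rule concerns cervical preparation, and the documents do not tie pain to gestational age.
- *That obstetric history belongs in the model too.* The plan collects it but does not link it to either outcome. A specific item such as prior vaginal delivery is not listed as a recorded field.
- *That gestational age will not be recorded.* The baseline list is not exhaustive, and both eligibility and the dilator thresholds require gestational age. Its absence is a matter of wording.

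**Conclusion.** The point holds in a limited form. For cervical dilation the plan prespecifies no covariate, while its own dilator rule gives a reason to expect variation with gestational age, a characteristic that eligibility already requires and the study drug cannot change. Including it would be valid and would probably help somewhat.

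The gain rests entirely on the assumed R²: a standard error about 2% to 16% smaller for R² between 0.05 and 0.30, against a loss of about 0.8% if gestational age explains nothing. The figures also assume that dilation is measured in all 66 women and that its relation to gestational age is roughly linear and similar in the two arms. There is no bias, and no effect on the primary conclusion. This is a worthwhile refinement, not an error in the plan.

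**What to change.** In the section 1.1.10 table, replace the entry for cervical dilation with a linear regression on study arm and gestational age in days on procedure day. State that the gestational-age term is used whether or not the arms differ on it at baseline. Add gestational age to the listed baseline data.

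The same term may be used in the VAS pain model for consistency, with the note that the documents give less support for it there.

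The cost is a change of wording and one residual degree of freedom out of 64. No new data, visits or participants are needed, and the primary analysis stays as it is.
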